Signed copies of this page containing the signature of the study center's principal investigator are stored in the sponsor's study file and in the respective center's investigator site file.

Synopsis - amended

Title	Multicenter, randomized, double-blind, double-dummy, active-comparator, event-driven, superiority phase III study of secondary prevention of stroke and prevention of systemic embolism in patients with a recent Embolic Stroke of Undetermined Source (ESUS), comparing rivaroxaban 15 mg once daily with aspirin 100 mg (NAVIGATE ESUS)
Short title	Secondary prevention of stroke in patients with ESUS
Clinical study phase	III
Study objectives	
The primary efficacy objective is:
 
 To evaluate whether rivaroxaban is superior to aspirin in reducing the risk of recurrent stroke and systemic embolism in patients with a recent ESUS 
The secondary efficacy objective is:
 
 To evaluate whether rivaroxaban is superior to aspirin in reducing cerebrovascular events, cardiovascular events, and mortality in patients with a recent ESUS 
The safety objective is to document the incidence of clinically relevant bleeding

Study medication	Rivaroxaban 15 mg (immediate-release film-coated tablets), or Aspirin 100 mg (enteric-coated tablets)
Type of control	Double dummy: Matching placebo will be provided for rivaroxaban and aspirin
Route of administration	Study medication is administered orally once daily and should be taken with food
Indication	Secondary prevention of stroke and prevention of systemic embolism in patients with a recent ESUS

Diagnosis and main criteria for inclusion	
Recent ESUS (between 7 days and 6 months), defined as:
 
 • Recent ischemic stroke (including transient ischemic attack with positive neuroimaging) visualized by brain imaging that is not lacunar, and • Absence of cervical carotid atherosclerotic stenosis > 50% or occlusion¹, and • No atrial fibrillation after \geq 24-hour cardiac rhythm monitoring (at least 20 hours acceptable)², and • No intra-cardiac thrombus on either transesophageal or transthoracic echocardiography,³ and • No other specific cause of stroke (for example, arteritis, dissection, migraine/vasospasm, drug abuse)
Study design	
Multicenter, randomized, double-blind, double-dummy, active-comparator, event-driven, superiority phase III study

Methodology	
Patients who fulfill all inclusion and none of the exclusion criteria after giving informed consent will be randomly allocated 1:1 to either rivaroxaban 15 mg or aspirin 100 mg orally once daily. Randomization will be stratified by country and age <60 and \geq60 years. ⁴
 
At randomization, patients will receive study medication and instructions for its administration. Thereafter, patients will return to the clinic at 1, 6, and 12 months and then every 6 months until the end of study (efficacy cut-off date) is announced. At 3 months, patients will be contacted by telephone. Throughout the study and at clinic visits, patients will be assessed for efficacy (stroke, systemic embolism, myocardial infarction, cardiovascular death, and all-causes mortality) and safety vital signs, bleeding, serious adverse events which are not outcome events, pregnancies, non-serious adverse events leading to permanent study drug discontinuation, and any non-serious adverse events of particular concern to the investigator).
 
Suspected clinical study outcomes (efficacy and bleeding) will be assessed by an Independent Central Adjudication Committee blinded to treatment allocation. Adjudicated results will be the basis for the final analyses.
 
The study is event-driven and thus, all patients will be treated (or followed-up in case of permanent discontinuation of study medication) until the required approximately 450 confirmed primary efficacy outcomes are expected to have occurred.
 
An Independent Data Monitoring Committee will monitor patient safety during the study and give recommendations to the Steering Committee.

¹ Prior to global Protocol Amendment 5, stenosis was \geq 50%.

² The phrase in parentheses was added with global Protocol Amendment 5 to reflect routine practice.

³ “Transesophageal” was added with global Protocol Amendment 5.

⁴ The following statement was deleted with global Protocol Amendment 5: “No more than 10% of the total patient population will be randomized into the age group <60 years.” See Section 13.1 for details.

Number of subjects	
The study is event-driven and it is estimated that approximately 7000 patients (3500 per treatment group) are to be enrolled in order to have 450 patients experiencing a positively adjudicated primary efficacy outcome event.
 
The number of patients enrolled in the total study may be adjusted or enrollment in the age group 50-59 years may be stopped based on a blinded review of the observed overall event rate of confirmed primary efficacy outcomes during the study.⁵

Primary variable	
Time from randomization to first occurrence of any of the components of the composite outcome (adjudicated); including:
 
 • Stroke (ischemic, hemorrhagic, and undefined stroke, transient ischemic attack with positive neuroimaging) • Systemic embolism
Plan for statistical analysis	
The primary efficacy analyses will be based on the intent-to-treat population. Rivaroxaban treatment will be compared with the aspirin control group using a stratified log-rank test. Kaplan-Meier curves for the cumulative incidence risk and cumulative incidence functions will be provided to evaluate the timing of event occurrence. Risk reduction will be estimated with the stratified Cox proportional hazards model.
 
Secondary efficacy outcomes will be analyzed using similar methods as for the primary efficacy analysis. Testing will be performed in hierarchical order.
 
There will be 2 formal interim analyses to assess efficacy and stop for overwhelming superiority, which will occur when approximately 50% and 67% of the planned primary efficacy outcomes have accrued.⁶
 
The analysis of the safety outcomes will be similar to those described for the primary efficacy outcome.

Anticipated total study duration and study duration per patient	
Total study duration: ~3 years Randomization period: ~2 years Treatment duration of last patient randomized: ~1 year Mean treatment duration per patient: ~2 years
 
The study is event driven and these timelines may vary depending on the enrollment rate and event rate in the study.

⁵ Sentence was revised with global Protocol Amendment 5. See Section 13.1 for details.

⁶ A second interim analysis was added with global Protocol Amendment 5. See Section 13.1 for details.

Table of procedures – amended ⁷

	Screen	Random	Treatment Phase						Washout
	V1	V2	V3	V4	V5	V6	V7-V [∞]	EOT ^a	Safety Visit
Timelines	-6 to 0 wks ^b	0	1 Mo	3 Mo	6 Mo	12 Mo	every 6 Mo	End of Treat	1 Mo post EOT
Visit Window (weeks)			±1	±4	±4	±4	±4		±1
Type of Visit	Visit	Visit	Visit ^L	☎	Visit	Visit	Visit	Visit	☎
Initiation procedures									
Informed consent	•								
Eligibility criteria	•								
Demographics	•								
Medical history and stroke risk factors	•								
Treatment and diagnosis of stroke ^c	•								
Pregnancy test ^d	•								
eGFR ^e	•								
Weight/height ^f	•					•	□		
Medication									
ConMeds ^g		•				•	□	•	
1 st study drug		•							
Drug dispense		•			•	•	•	•	
Drug return + accountability					•	•	•	•	
Efficacy/Safety Outcomes ^h			← continuous reporting →						
Safety			← continuous reporting →						
Adverse events ⁱ									
Vital signs ^j		•			•	•	□	•	
Outcomes Research									
EQ-5D		•			•	•	•	•	
MoCA and SAGE		•				•		•	
Modified Rankin Score ^k	•					•		•	

Abbreviations: EOT = end of treatment; Mo = month; V = visit, ☎ = telephone contact; eGFR = estimated glomerular filtration rate; ConMeds = Concomitant medications; MoCA = Montreal Cognitive Assessment; SAGE = Standard Assessment of Global-Activities in the Elderly; EQ-5D = European Quality of Life-5 Dimensions questionnaire; SAE = serious adverse event; TIA = transient ischemic attack; MI = myocardial infarction

- End of treatment visit is to be performed within the trial close-out window before the end of the study (efficacy cut-off date) or once the patient has permanently discontinued study medication and when no further visits at the site will be performed
- Screening visit can be the same as randomization visit, if all required tests for eligibility criteria are available at screening visit. Maximum screening period 6 weeks.
- Acute and chronic therapy of stroke (for example [e.g.], thrombolysis, aspirin [ASA]) and diagnostic tests performed to diagnose acute stroke and Embolic Stroke of Undetermined Source (ESUS) as well as National Institutes of Health Stroke Score (NIHSS)

⁷ Global Protocol Amendment 5 made the following changes to this table: the Digit Symbol Substitution (DSS) test was removed; the window for Visit 1 was extended 2 weeks; footnotes a, b, and k were revised; and footnote L was added. See Section 13.1 for details.

-
- d Only in women of childbearing potential (local urine or serum pregnancy test)
 - e Creatinine to be measured at the local laboratory at screening, unless conducted within 1 month prior to screening. The eGFR may be recorded as reported by the local laboratory or otherwise should be calculated using Modification of Diet in Renal Disease (MDRD) formula. A calculator may be found at www.mdrd.com. During the study creatinine and eGFR should be measured according to local practice.
 - f Height to be measured only at screening
 - g Concomitant medications and the changes need to be documented only at the specified visits for chronic cerebro- and cardiovascular treatments. In addition, treatments for SAEs and outcome events must be reported.
 - h All potential outcome events including recurrent stroke, TIA, systemic embolism, MI, hospitalizations for cardiac chest pain, deaths, and bleeding must be reported on an ongoing basis even if the patient is permanently discontinued from study treatment. Healthcare resource use will be documented for all endpoints. See Section [7.6.1.1](#)
 - i Only SAEs not exempted from SAE reporting, pregnancy, non-serious AE leading to permanent discontinuation, and non-serious AEs of particular concern to the investigator need to be reported. See Section [7.5.3.2](#).
 - j Blood pressure and heart rate
 - k For definition see Section [7.6.1.4](#). In case of recurrent stroke to be done at 7 days post stroke or at discharge from hospital in case this occurs before 7 days and again at 3-6 months post stroke
 - L Patients who are at a rehabilitation or other clinic at the time of the 1 month visit (Visit 3), more flexibility will be allowed and this visit can be performed as a phone call instead of an onsite visit.
 - To be performed at specified visits
 - To be performed only once per year

Table of contents

Title page	2
Signature of Bayer's medically responsible person	3
Signature of the principal investigators for the study	3
Signature of the principal investigator at the study site	4
Synopsis - amended	5
Table of contents	10
Table of figures	12
List of abbreviations	13
1. Introduction	16
1.1 Background	16
1.2 Embolic stroke of undetermined source	16
1.3 Studies assessing the efficacy of anticoagulation for secondary prevention of embolic stroke of undetermined source - amended	17
1.4 Efficacy and safety of rivaroxaban in patients with prior stroke	17
1.5 Current guideline recommendations and dose of aspirin	19
1.6 Study rationale	19
1.7 Dose rationale	20
1.8 Benefit/risk assessment	20
2. Study objectives	21

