8.4.2 Analysis of secondary efficacy variables

The secondary efficacy outcomes will be ordered and tested in a sequential manner as listed in Section 7.3.3.2

If the superiority of rivaroxaban for the primary outcome is declared, the following alternative hypotheses, superiority of rivaroxaban compared with ASA for the secondary efficacy outcomes will be tested in the sequential order. That is, the subsequent ordered secondary outcome will be tested only if superiority can be shown for the previous outcomes. If an individual test during any step is not statistically significant, further testing may continue but significance will not be claimed. This hierarchical testing procedure will control the global Type 1 error level.

The analysis methods will be similar to those described for the primary efficacy outcome.

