8.5 Planned interim analyses - amended

⁴³The IDMC will monitor the study for greater than expected efficacy and for safety. There will be 2 formal interim analyses to assess efficacy, which will occur when approximately 50% and 67% of the planned primary efficacy events have accrued. The IDMC may recommend early study termination at these interim analyses, if there is overwhelming superiority of rivaroxaban ($Z > 4$) for efficacy. Also, secondary efficacy and safety will be considered. The study will be stopped early if the totality of data suggests an overwhelming benefit of rivaroxaban over ASA.

The IDMC has the flexibility to initiate further interim analyses after the first formal efficacy analysis at 50%, if deemed appropriate. Given the conservative nature of the monitoring guidelines used in the trial, no adjustment of the significance level for the final analysis is required.

The execution of the interim analyses and decision rules will be specified in the IDMC charter.

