### 6.2.5 Analysis of secondary efficacy variables

A single primary efficacy outcome will maintain strict control of the type I error rate. If the primary efficacy outcome is statistically significant, the secondary efficacy outcomes will be tested in a sequential manner according to the order as listed in section 6.2.2.

If the superiority of rivaroxaban for the primary outcome is declared, the following alternative hypotheses, superiority of rivaroxaban compared with ASA for the secondary efficacy outcomes will be tested in the sequential order. That is, the subsequent ordered secondary outcome will be tested only if superiority can be shown for the previous outcomes.

If an individual test during any step is not statistically significant, further testing may continue but significance will not be claimed. This hierarchical testing procedure will control the global Type 1 error level.

The primary analysis of the secondary variables will include events as adjudicated by the ICAC and will be based on the ITT analysis set using the ITT data scope.

The first secondary efficacy variable (SE1) of this study is the time from randomization to first occurrence of cardiovascular death (including death due to hemorrhage), recurrent stroke, systemic embolism, or MI. The following null hypothesis will be tested at the significance level of 0.025:

$H_{0, SE1}: S_{R1}(t) = S_{A1}(t)$  for all time points  $t \geq 0$ ,

The one-sided alternative hypothesis will be:

$H_{1, SE1}: S_{R1}(t) > S_{A1}(t)$  for at least one time point  $t \geq 0$ , and  $S_{R1}(t) \geq S_{A1}(t)$  for all time points  $t \geq 0$ ,

where  $S_{R1}$  denotes the survival function of the rivaroxaban and  $S_{A1}$  denotes the survival function of the ASA group.

The second secondary efficacy variable (SE2) of this study is the time from randomization to first occurrence of death from any cause. The following null hypothesis will be tested at the significance level of 0.025:

$H_{0, SE2}: S_{R2}(t) = S_{A2}(t)$  for all time points  $t \geq 0$ ,

The one-sided alternative hypothesis will be:

$H_{1, SE2}: S_{R2}(t) > S_{A2}(t)$  for at least one time point  $t \geq 0$ , and  $S_{R2}(t) \geq S_{A2}(t)$  for all time points  $t \geq 0$ ,

where  $S_{R2}$  denotes the survival function of the rivaroxaban and  $S_{A2}$  denotes the survival function of the ASA group.

The analysis methods will be those described for the primary efficacy outcome.

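### Secondary outcomes have no interim boundary of their own, so the stated control of the global type I error fails modestly if the trial stops early for efficacy

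*Protocol*

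**What the plan says.** The Protocol synopsis (Plan for statistical analysis) announces the efficacy interims, "There will be 2 formal interim analyses to assess efficacy and stop for overwhelming superiority", and says of the secondary outcomes: "Testing will be performed in hierarchical order". Protocol 8.4.2 sets out the fixed sequence and concludes: "This hierarchical testing procedure will control the global Type 1 error level". SAP 6.2.5 repeats that conclusion.

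SAP 6.2.5 opens the sequence with the condition "If the superiority of rivaroxaban for the primary outcome is declared". For the first secondary (the composite of CV death, stroke, systemic embolism and MI) it says "The following null hypothesis will be tested at the significance level of 0.025", and it gives the same level for all-cause mortality. The remaining secondaries get the same analysis.

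Protocol 8.5 places the interims by event count, "which will occur when approximately 50% and 67% of the planned primary efficacy events have accrued", and says "The IDMC may recommend early study termination at these interim analyses, if there is overwhelming superiority of rivaroxaban", with Z > 4 as the criterion. SAP 4.4 agrees and makes clear that this Z belongs to the primary outcome. For secondary efficacy at an interim, both sections say only that it will be considered. Both let the IDMC add looks after the 50% analysis, both state that "no adjustment of the significance level for the final analysis is required", and both leave execution and decision rules to the IDMC charter.

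**The concern.** The condition that opens secondary testing is not limited to the final analysis, and only one level is given. Read as written, if the primary crosses Z > 4 at 50% or 67% of events, the first secondary is then tested against 1.96 at that look. If the primary does not cross, the secondary is tested against 1.96 at the end.

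A very strict interim bound spends almost none of the primary's alpha, and that is what justifies leaving the final level unadjusted. It does nothing for a secondary. The look at which the secondary is tested is selected by an extreme value of a positively correlated statistic, so a null secondary is more likely than usual to be high at that look. A fixed sequence combined with a group-sequential primary has strong control only if each secondary also has a valid stage-wise boundary.

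At stake is a claim on a secondary outcome after an early efficacy stop, made under an error rate that the documents state but the rules do not deliver.

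**Working it through.** **Inputs from the documents.** 450 primary events; 1:1 allocation; one-sided 0.025; 90% power; expected observed risk reduction 26%, i.e. hazard ratio 0.74 (Protocol 8.6, SAP 4.6; allocation from Protocol 6.3). Looks at information 0.50, 0.67 and 1.00; primary bounds 4, 4 and 1.96 (Protocol 8.4.1 and 8.5).

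**Assumptions.** The documents give no correlation (rho) between the primary and secondary test statistics, so it is varied. Both outcomes have the same information fractions. Crossing Z > 4 always stops the trial. In the main calculation no events accrue after the stop.

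**The plan's own figure.** Drift = (√450 / 2) × (−ln 0.74) = 10.607 × 0.3011 = 3.194. Power = Φ(3.194 − 1.960) = Φ(1.234) = 0.891, which agrees with 90%.

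**Primary alpha.** Recursive integration with bounds 4 / 4 / 1.96 gives 0.00003 + 0.00002 + 0.02495 = 0.0250. With four further Z > 4 looks it is still 0.0250.

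**Chance of an efficacy stop at hazard ratio 0.74.** First look: 1 − Φ(4 − 3.194 × √0.5) = 1 − Φ(1.742) = 0.041. Second look, by simulation: 0.051. Together about 9.2%.

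**Null first secondary.** In 4 million simulated pairs of correlated Brownian paths, the secondary has zero drift and is tested at 1.96 at whichever look the primary first succeeds:

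| rho | Error at hazard ratio 0.74 | Largest error over primary effects tried |
|---|---|---|
| 0 | 0.0223 | 0.0250 |
| 0.3 | 0.0258 | 0.0271 |
| 0.5 | 0.0280 | 0.0289 |
| 0.8 | 0.0332 | 0.0332 |
| 0.95 | 0.0376 | 0.0386 |
| 1.0 | 0.0379 | 0.0430 |

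The level of 0.025 is exceeded at every correlation of 0.3 or more that was examined. Since rho is roughly the square root of the share of secondary events that are also primary events, an assumed share of 70% gives √0.7 = 0.84, where the error is 0.034.

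**Overrun.** If further events accrue before the cut-off, amounting to 5%, 10% or 15% of full information (assumed), the error at rho 0.84 falls from 0.034 to 0.033, 0.031 and 0.030. At rho 0.3 it falls to 0.025–0.026.

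**With the fix.** An upper limit on the secondary's error is the chance that it crosses its own bound at any look. That is 0.0251 with bounds 3.29 / 3.29 / 1.96 and 0.0250 with 4 / 4 / 1.96, whatever the correlation. With 4 / 4 / 1.96 the largest simulated error was 0.0200, 0.0210, 0.0229 and 0.0250 at rho 0, 0.5, 0.8 and 1.

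**The case against.** Several points on the other side stand.

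- **The premise is inferred.** No sentence says that secondaries are tested at 0.025 on interim data. It follows from an unrestricted condition and the absence of any other level. The charter might contain a rule, although the secondary testing rule and the error claim sit in the protocol and SAP.
- **Overrun.** SAP 4.5.2 counts events up to the efficacy cut-off date, not to an interim snapshot. This reduces the inflation, as shown above.
- **The upper values are strained.** With a 70% overlap and a hazard ratio of 0.74 on stroke and systemic embolism, a null composite needs a hazard ratio of about (1 − 0.7 × 0.74) / 0.3 = 1.6 on the other events (CV death, MI). At 90% overlap (rho about 0.95) it needs (1 − 0.9 × 0.74) / 0.1 = 3.3. Protocol 8.5 has the IDMC weigh secondary efficacy and safety, so such harm would argue against stopping, whereas the simulation stops mechanically.
- **The IDMC's freedom to add looks leaves the primary intact.** Its effect on the secondaries was not calculated.

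A reader might infer that the trial's overall error rate is broken. It is not: the primary alpha and the error under the global null are both 0.025. A reader might also infer that a secondary claim after an efficacy stop is usually unreliable. Given a stop, the false-positive rate at the first and second look is 39% and 18% at rho 0.84, but 16% and 10% at rho 0.5, and 9% and 7% at rho 0.3. These rates condition on an event of about 9% probability, and the plan claims no conditional error rate.

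None of this restores the claim. A positive correlation is to be expected, because the whole primary composite is nested in the first secondary, and the unconditional error then exceeds 0.025 under the plan's own assumed effect.

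**Conclusion.** The claim of global type I error control is wrong as written for a declaration of superiority at an interim. Strong control fails when the primary effect is real and a correlated secondary is null. The unconditional excess is modest: about 0.1 to 1.3 percentage points over 0.025 at the design effect for correlations of 0.3 to 0.95, and 1.8 points in the worst case found. These figures rest on assumed correlations, equal information fractions, no overrun and a mechanical stop at Z > 4. For a weakly correlated outcome (rho 0.3) the error is at most about 0.027.

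The defect does not depend on there being two interims; one would already create it.

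It is a defect of the plan only. The SAP introduction records that the trial was stopped for excess bleeding without offsetting benefit, so the efficacy-stop route was never used. The documents give no support for reading this point as casting doubt on the trial's result.

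**What to change.** In SAP 4.4 and 6.2.5, and in Protocol 8.4.2 and 8.5, state that if primary superiority is declared at any interim, planned or added, a secondary outcome is claimed, in sequence, only if its own Z exceeds a stage-wise bound: for example 3.29, or 4 as for the primary. The 1.96 bound is kept for the planned final analysis. If the charter already contains such a rule, bring it into the SAP.

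The alternative is to limit the sentence on type I error control to the planned final analysis.

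The first option costs one sentence and leaves the final level unchanged. Its downside is fewer secondary claims, and only after an early efficacy stop. Because this trial has already stopped for another reason, the change would alter none of its analyses. It corrects the stated property and would serve a later design that reuses this wording.
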